#### Statistical Analysis Plan

			•	Overall improvement of document structure, language and consistency
2.1	13MAR2024	[name]	•	Windowing conventions updated. There was
		[name],		an issue with some of the scheduled days.
		[name]		Now all of them are calculated as follows:
		[name]		floor (Study Month Number * 30.4).

Document: Statistical Analysis Plan: AEGR-734-401: A 36-Month, Multicenter, Open Label Phase 4 Study to Evaluate the

Immunogenicity of Daily SC Metreleptin Treatment in Patients with Generalized Lipodystrophy

Author: [name], [name], [name], [name] Version Number: 2.1

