#### 20. APPENDIX 2. WINDOWING CONVENTIONS

The below windowing conventions will be used to categorize all study assessments, including assessments occurring during unscheduled visits, into time periods of interest. Days are counted from the date of baseline visit where Baseline is defined as Day 0.

Only one assessment of each type will be presented from each analysis window. If more than one assessment of the same type occurs within an analysis window, then the maximum severity result will be selected for presentation. If more than one assessment of each types occurs within the maximum severity category, the result closest to the end of the analysis window will be selected. If the concept does not apply, then the result closest to the end of the analysis window will be selected.

The result closest to the end of the analysis window is preferred since the end of the analysis window aligns with the end of the visit window in all cases while the beginning of the analysis window may precede the beginning of the visit window. Therefore, the result closest to the end of the analysis window is most likely to be within the visit window.

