### Changes documented in 16Dec2024 version (prior to DBL)

1. Update definition of EAS from:

[E]nrolled subjects who received at least one documented dose of metreleptin and who have baseline and post-dose laboratory results on the measure of interest at the time point of interest.

To:

Enrolled subjects who received at least one documented dose of metreleptin and who have at least one anti-metreleptin/anti-HuL binding antibody (Antidrug Antibody (ADA) binding) result.

2. Update the following analysis from:

AEs, serious AEs (SAEs), AEs of special interest (AESIs), TEAEs, AEs possibly caused by metreleptin, and AEs leading to metreleptin discontinuation will be summarized by ADA positivity and titer, cell-based NAb positivity and titer, and RB positivity, titer, and quintile of percent inhibition.

To:

TEAEs, serious TEAEs, TEAEs that are AEs of special interest (AESIs), TEAEs possibly caused by metreleptin, and TEAEs leading to metreleptin discontinuation will be summarized by ADA positivity and titer, cell-based NAb positivity and titer, and RB positivity, titer, and quintile of percent inhibition.

3. Update analysis windows such that data collected for a CRF-defined visit are windowed according to the CRF-defined visit. Previously analysis windows ended on the same day as CRF-defined visit windows and extended CRF-defined windows to cover the calendar space since the last CRF-defined visit. Analysis windows are updated to extend CRF-defined visit windows to cover calendar space on either side of the CRF-defined visit window. See updated windows in Table 1 below.

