### **Table 1: Updated Visit Windows**

Study Visit	Study Month	Protocol Specified Visit Window	Analysis Window
Visit 1 (Screening)	Month -1	Day -28 to Day 0	Day ≤ -1
Visit 2 (Baseline)	Month 0	Day 0	Day 0
Visit 3	Month 1	Day 23 to Day 37	Day 1 to Day 44
Visit 4	Month 2	Day 53 to Day 67	Day 45 to Day 90
Visit 5	Month 4	Day 114 to Day 128	Day 91 to Day 151
Visit 6	Month 6	Day 175 to Day 189	Day 152 to Day 227
Visit 7	Month 9	Day 266 to Day 280	Day 228 to Day 314
Visit 8	Month 12	Day 350 to Day 378	Day 315 to Day 455
Visit 9	Month 18	Day 533 to Day 561	Day 456 to Day 637
Visit 10	Month 24	Day 715 to Day 743	Day 638 to Day 820
Visit 11	Month 30	Day 898 to Day 926	Day 821 to Day 1002
Visit 12	Month 36	Day 1080 to Day 1108	Day ≥ 1003

Describe the process used to decide on the change(s) and who was involved:

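### The SAP's end-of-window tie-break no longer fits the December 2024 windows: where severity does not order results, a late unscheduled value can replace the on-time scheduled one

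*SAP*

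**What the plan says.** SAP v2.1, Appendix 2 (Windowing Conventions), covers all assessments, including those from unscheduled visits, and allows one result of each type per analysis window. Selection has three parts:

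- With more than one result in a window, "then the maximum severity result will be selected for presentation".
- Ties at that top severity level go to whichever result lies nearest the window's end.
- Where severity has no meaning for the measure, the same end-of-window preference decides: "the result closest to the end of the analysis window will be selected".

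The appendix defends the end-of-window preference on one ground, that "the end of the analysis window aligns with the end of the visit window in all cases". It reasons that the latest result is therefore the one most likely to lie inside the visit window.

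Item 3 of the change form's 16Dec2024 entry (before database lock) makes two changes. Data from a CRF-defined visit are kept with that visit. In addition, "Analysis windows are updated to extend CRF-defined visit windows to cover calendar space on either side of the CRF-defined visit window". The form's Table 1 gives the new limits; Month 12, for example, becomes "Day 315 to Day 455", against a visit window of Day 350 to Day 378. The text of item 3 does not mention the selection rule or its rationale.

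**The concern.** The tie-break depended on a property of the windows that the December 2024 update removed. With windows ending at the visit window's end, taking the latest result tended to protect the scheduled value. With windows running weeks or months past the visit, the same words favour whichever unscheduled result came later.

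The displacement would not be random for every measure. Protocol sections 7.3.1 and 7.4.1 call for extra antibody and leptin samples when clinically indicated, such as at loss of response or severe infection. A value drawn because something went wrong could then stand in a by-visit table as the Month 12 value. The study plans ten patients (Protocol 4.2) or eleven (SAP 4.1), so one replaced value is 1/10 = 10% or 1/11 = 9.1% of the patients behind a by-visit summary.

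**Working it through.** **Inputs.** Month numbers and visit tolerances come from Protocol Table 1 (±7 days through Month 9, ±14 days from Month 12). The SAP modification history for v2.1 sets the scheduled day at floor(month × 30.4). The v2.1 windows are in SAP Appendix 2, Table 2, and the December 2024 windows in the change form's Table 1.

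**Reproducing the plan's figures.** Scheduled day ± tolerance should give the stated visit windows. Month 12: floor(12 × 30.4) = floor(364.8) = 364, and 364 ± 14 = Day 350 to Day 378, as stated. All ten post-baseline visit windows reproduce exactly.

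**Checking the rationale under v2.1.** Analysis window end minus visit window end is 0 for Months 1 to 30. Month 36 is open-ended (Day 927 onward, against a visit window ending on Day 1108), so the claim already failed there.

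**Checking it under the December 2024 windows.**

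| Month | Scheduled day | Visit window end | New analysis window end | Past visit window | Past scheduled day |
|---|---|---|---|---|---|
| 1 | 30 | 37 | 44 | 7 | 14 |
| 2 | 60 | 67 | 90 | 23 | 30 |
| 4 | 121 | 128 | 151 | 23 | 30 |
| 6 | 182 | 189 | 227 | 38 | 45 |
| 9 | 273 | 280 | 314 | 34 | 41 |
| 12 | 364 | 378 | 455 | 77 | 91 |
| 18 | 547 | 561 | 637 | 76 | 90 |
| 24 | 729 | 743 | 820 | 77 | 91 |
| 30 | 912 | 926 | 1002 | 76 | 90 |
| 36 | 1094 | 1108 | none (from Day 1003) | no limit | no limit |

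No post-baseline analysis window now ends with its visit window. Under v2.1 a bounded window ended at most 14 days after the scheduled day.

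**What this does to selection.** Take a measure with no severity order, scheduled results on Days 364 and 547, and an unscheduled result on Day 450 (hypothetical days).

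- v2.1: Day 450 falls in the Month 18 window (379 to 561). Day 547 is 561 − 547 = 14 days from the end and Day 450 is 561 − 450 = 111 days from it. Both scheduled values are reported.
- December 2024: Day 450 falls in the Month 12 window (315 to 455). It is 455 − 450 = 5 days from the end and Day 364 is 455 − 364 = 91 days from it. The unscheduled value is reported as Month 12.

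**Which summaries are exposed.** Where the maximum rule orders results by titer or category, tied results share that titer or category, so choosing the later one leaves the by-visit table unchanged. The exposure lies with measures that have no order: receptor-blocking percent inhibition by visit (SAP 15.2) and leptin by visit and as change from baseline (SAP 18.2). HbA1c, fasting glucose and triglycerides join them if treated as unordered; the SAP does not say.

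**The case against.** The case against has several sound parts.

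- **Severity comes first.** A reader might infer that the rule now always takes the latest result, or that it distorts by-visit titers. Neither follows. The end-of-window step acts only on ties or where severity does not apply. Maximum titer by visit is also the protocol's own summary (Protocol 10.4 and 10.5).
- **Event-driven HbA1c or triglycerides are not documented.** The triggered extra samples are for antibodies, neutralizing activity and leptin (Protocol 7.3.1, 7.4.1, 8.3.8). Triglyceride monitoring outside visits appears only for dose tapering (Protocol 4.11.1). The event-driven argument therefore cannot be carried over to those measures.
- **Scheduled data stay with their CRF visit.** The date windows therefore mainly place unscheduled results, and a problem needs a later unscheduled result of the same type in the same window. This limits how often it can happen. It does not remove the problem, because item 3 gives the scheduled result no priority once both share a window.
- **The new windows improve placement in one respect.** The v2.1 windows reached back as far as 547 − 379 = 168 days before the scheduled day (Month 18; also Month 30, 912 − 744 = 168). The largest bounded distance is now 91 days. That supports the new windows, not the unrevised tie-break.
- **Several key summaries do not use the rule.** Ever-positive, time-to-positivity and peak results are defined from dated results (SAP 15.2), and adverse events are linked to the most recent prior measurement (SAP 17.1).
- **Part of the change form was not available.** A revised selection rule there cannot be excluded.

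**Conclusion.** The point stands in limited form. The only stated reason for preferring the end of the window is false for every post-baseline window in the December 2024 table: by 7 to 77 days past the visit window at Months 1 to 30, or 14 to 91 days past the scheduled day. The 91-day figure belongs to Months 12 and 24 only; Months 18 and 30 reach 90 days, and through Month 9 the range is 14 to 45. A reader might also count Month 36 as a consequence of the update, but it was already open-ended in v2.1.

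Following the visible rule gives a less representative by-visit value for any measure without a severity order, whenever a later unscheduled result shares the window with an on-time scheduled one. How often that occurs cannot be told from the documents. The analyses are descriptive, with no hypothesis testing (SAP 8.1), so the consequence is misplaced values in by-visit and change-from-baseline summaries. The conclusion assumes that the unavailable pages of the change form leave the selection rule as it stands in Appendix 2.

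**What to change.** Amend the selection rule in Appendix 2, or in the change form:

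1. Keep the maximum rule for antibody titers and neutralizing categories.
2. For all other measures, select the CRF-scheduled visit result. If there is none, select the result closest to the scheduled day, floor(month × 30.4). This also works at Month 36 (Day 1094), where the open window has no end to be close to.
3. State which measures are severity-ordered, naming percent inhibition, leptin, HbA1c, glucose and triglycerides explicitly.
4. Delete the outdated rationale sentence.
5. Show unscheduled results in listings, so that event-driven values remain visible.

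The cost is a few sentences and minor reprogramming. The change form already carries an entry dated 26Feb2025 after database lock; a correction made after lock must likewise be recorded as post-lock. If the unavailable pages already revise the rule, it is enough to cite that revision and remove the old rationale.

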**Table 2: Windowing conventions** 

Study Visit	Study Month	Protocol Specified Visit Window	Analysis Window
Visit 1 (Screening)	Month -1	Day -28 to Day 0	Day ≤ -1
Visit 2 (Baseline)	Month 0	Day 0	Day 0
Visit 3	Month 1	Day 23 to Day 37	Day 1 to Day 37

Document: Statistical Analysis Plan: AEGR-734-401: A 36-Month, Multicenter, Open Label Phase 4 Study to Evaluate the

Immunogenicity of Daily SC Metreleptin Treatment in Patients with Generalized Lipodystrophy

Author: [name], [name], [name], [name] Version Number: 2.1

Page 25 of 25

#### Statistical Analysis Plan

Study Visit	Study Month	Protocol Specified Visit Window	Analysis Window
Visit 4	Month 2	Day 53 to Day 67	Day 38 to Day 67
Visit 5	Month 4	Day 114 to Day 128	Day 68 to Day 128
Visit 6	Month 6	Day 175 to Day 189	Day 129 to Day 189
Visit 7	Month 9	Day 266 to Day 280	Day 190 to Day 280
Visit 8	Month 12	Day 350 to Day 378	Day 281 to Day 378
Visit 9	Month 18	Day 533 to Day 561	Day 379 to Day 561
Visit 10	Month 24	Day 715 to Day 743	Day 562 to Day 743
Visit 11	Month 30	Day 898 to Day 926	Day 744 to Day 926
Visit 12	Month 36	Day 1080 to Day 1108	Day ≥ 927

Document: Statistical Analysis Plan: AEGR-734-401: A 36-Month, Multicenter, Open Label Phase 4 Study to Evaluate the

Immunogenicity of Daily SC Metreleptin Treatment in Patients with Generalized Lipodystrophy

Author: [name], [name], [name], [name] Version Number: 2.1

### The timing of the change(s) was:

After authorization (signed version) of the SAP but prior to the database lock/interim data cut/ final Statistical Report/ Clinical Study Report (CSR)

After database lock/ interim data cut/ final Statistical Report/ CSR

Form No: RWI FM BIOS0027 Revision 2 Reference: RWI WI BIOS0015

Page 2 of 10

Client: Chiesi

 Protocol No.:
 AEGR-734-401

 Project Code:
 DYA76668

 Date:
 26-Feb-2025

Describe the change(s) required:

Form No: RWI\_FM\_BIOS0027 Revision 2 Reference: RWI\_WI\_BIOS0015

Page 3 of 10

Client: Chiesi

 Protocol No.:
 AEGR-734-401

 Project Code:
 DYA76668

 Date:
 26-Feb-2025

### Changes documented in 16Dec2024 version (prior to DBL)

1. Update definition of EAS from:

[E]nrolled subjects who received at least one documented dose of metreleptin and who have baseline and post-dose laboratory results on the measure of interest at the time point of interest.

To:

Enrolled subjects who received at least one documented dose of metreleptin and who have at least one anti-metreleptin/anti-HuL binding antibody (Antidrug Antibody (ADA) binding) result.

2. Update the following analysis from:

AEs, serious AEs (SAEs), AEs of special interest (AESIs), TEAEs, AEs possibly caused by metreleptin, and AEs leading to metreleptin discontinuation will be summarized by ADA positivity and titer, cell-based NAb positivity and titer, and RB positivity, titer, and quintile of percent inhibition.

To:

TEAEs, serious TEAEs, TEAEs that are AEs of special interest (AESIs), TEAEs possibly caused by metreleptin, and TEAEs leading to metreleptin discontinuation will be summarized by ADA positivity and titer, cell-based NAb positivity and titer, and RB positivity, titer, and quintile of percent inhibition.

3. Update analysis windows such that data collected for a CRF-defined visit are windowed according to the CRF-defined visit. Previously analysis windows ended on the same day as CRF-defined visit windows and extended CRF-defined windows to cover the calendar space since the last CRF-defined visit. Analysis windows are updated to extend CRF-defined visit windows to cover calendar space on either side of the CRF-defined visit window. See updated windows in Table 1 below.

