Study Population	Patients who have been prescribed metreleptin for treatment of these conditions will be enrolled in the study, prior to initiation of metreleptin treatment. Pediatric patients will be included since patients with congenital generalized lipodystrophy present with this condition at birth and patients with acquired generalized lipodystrophy often present during early childhood. Assessment of antibodies is required; thus, only patients who have not been previously treatment with metreleptin will be		

Confidential Page 11 of 60

	enrolled in order to document the development of antibodies	
	over time.	
Methodology/Study	MYALEPT [™] (metreleptin) has been approved as an adjunct to	
Design:	diet as replacement therapy to treat the complications of leptin deficiency in patients with congenital or acquired generalized lipodystrophy (MYALEPT Prescribing Information). This study is a multicenter, open-label, Phase 4 trial to provide an assessment of the immunogenicity associated with metreleptin and of any major potential risks due to development of antibodies to metreleptin. The study is being conducted to comply with the postmarketing requirement.	
	Patients who have been prescribed metreleptin for lipodystrophy, who meet all enrollment criteria and sign informed consent for this study at Screening (Visit 1) will receive the first dose of metreleptin at Enrollment/Baseline (Visit 2) at the study site. Patients will return to the study site for follow-up and collection of blood samples at regular intervals (at Months 1, 2, 4, 6, 9, 12, 18, 24, 30, and 36), for a total of 12 visits over 3 years (36 months). All patients with suspected loss of metreleptin efficacy (worsening of metabolic control) or endogenous leptin action (severe infections or sepsis) should be tested for in vitro	
Planned Number of Patients:	neutralizing activity. Ten patients who have been prescribed metreleptin will be enrolled.	
Study Population/ Inclusion Criteria:	For inclusion in the study, patients should fulfill the following criteria at the screening visit:	

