- 7. Creatinine clearance <30 mL/min using institutional standards:
 - e.g., calculated using Cockcroft-Gault formula for patients

Confidential Page 13 of 60

≥18 years of age;
calculated using Schwartz equation for patients <18 years
of age.

- 8. For women only currently pregnant (confirmed with positive pregnancy test) or breast-feeding.
- 9. Any condition where, in the opinion of the Investigator, participation in this study may pose a significant risk to the patient or could render the patient unable to successfully complete the study.

Test Product, Dose, Dosage Form, Mode of Administration:

Patients who have been prescribed metreleptin and are enrolled in the study will be administered metreleptin once daily by SC injection at doses consistent with the US prescribing information (see table below). Based on clinical response (e.g., inadequate metabolic control) or other considerations (e.g., tolerability issues, or excessive weight loss, particularly in pediatric patients), the dose may be decreased or increased to the maximum dosage (see table below).

Baseline weight	Starting daily dose (injection volume)	Dose adjustments (injection volume)	Maximum daily dose (injection volume)
≤40 kg (male and female patients)	0.06 mg/kg (0.012 mL/kg)	0.02 mg/kg (0.004 mL/kg)	0.13 mg/kg (0.026 mL/kg)
Male patients >40 kg	2.5 mg (0.5 mL)	1.25 mg (0.25 mL) to 2.5 mg (0.5 mL)	10 mg (2 mL)
Female patients >40 kg	5 mg (1 mL)	1.25 mg (0.25 mL) to 2.5 mg (0.5 mL)	10 mg (2 mL)

Duration of Treatment and Study Participation:

Development of neutralizing antibodies to metreleptin and HuL has been observed with metreleptin treatment. The time to the first sample in which Category D or E *in vitro* neutralizing activity was detected ranged from 20 weeks to 156 weeks following initiation of metreleptin treatment. In this study, immunogenicity will be assessed over 3 years (36 months) of continuous treatment to allow sufficient time to evaluate not only binding antibodies to metreleptin and HuL, but also potential *in vitro* neutralizing activity.

Confidential Page 14 of 60

Statistical Methods:	There will be no hypothesis testing. All data will be summarized by descriptive statistics and/or listing. The following will be used for all analyses:
	Patients treated with a dose of metreleptin will be included in the safety and tolerability and patients with a post dose sample will be assessed for immunogenicity

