6.2.2 Baseline/Enrollment Visit

At the Enrollment Visit (Visit 2), to be conducted within 28 days of the Screening Visit, patients are to have fasted overnight (8 hours). Patients should delay administering their morning dose of anti-diabetes therapy (if applicable) until enrollment procedures have been completed. All procedures specified in the Study Plan (Table 1) should be conducted prior to first administration of metreleptin. The following will be conducted at the Baseline/Enrollment visit:

- Inclusion and exclusion criteria will be verified.
- Blood samples for measurement of leptin and antibodies to metreleptin and human leptin will be collected to provide a measurement prior to initiation of metreleptin.
- Fasting samples for hematology and clinical chemistry will be collected.
- Samples for measurement of HbA1c, lipids and fasting glucose will be collected.
- Vital signs and weight will be measured.
- Concomitant use of lipid-lowering and anti-diabetic, will be reviewed.
- The Investigator will instruct the patient on proper reconstitution of metreleptin and have the patient or caregiver administer the first dose of metreleptin by SC injection under observation.
- Serious adverse events and AESI (refer to Section 8.3.8) will be reviewed.
- Urine pregnancy tests (βhCG) will be conducted for all female patients of childbearing potential.

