#### 6.3 **Effectiveness Analysis Set (EAS)**

The effectiveness analysis set (EAS) will contain all enrolled subjects who received at least one documented dose of metreleptin and who have baseline and post-dose laboratory results on the measure of interest at the time point of interest. By definition, the EAS will vary by both measure and timepoint. The effectiveness analysis sets will be used in the primary and exploratory analyses.

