#### 15. PRIMARY ANALYSIS – IMMUNOGENICITY

The primary immunogenicity analysis will be performed among the EAS. Analyses will be performed as described below. Additional data visualizations may be generated as needed.

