### 15.2 Primary Analysis Description, Derivations, and Definitions

The presence of anti-drug antibodies will be screened using an ADA binding assay, which detects antibodies to both Metreleptin and HuL, and reported as follows:

- Positive/negative for ADA binding by study visit. Positive ADA is defined as ADA binding detected at MRD (1:10 dilution factor). Both 90% and 80% two-sided Clopper-Pearson exact CIs will be presented.
- ADA binding by study visit and titer (negative [no ADA binding detected at MRD], 1:10, 1:50, 1:250, 1:1250, 1:6250, 1:31250). Dilution factors greater than 1:31250 will not be examined.
- Ever ADA positive and time to ADA positivity. Time to ADA positive result (months) = [((date of first ADA positive result date of baseline visit) + 1)/30.4].
- Peak ADA (defined as the measurement which detects ADA binding activity at the largest dilution factor) and time to peak ADA. Time to peak ADA (months) = [((date of peak ADA date of baseline visit) + 1)/30.4].

In vitro NAb activity will be measured in a cell-based assay and categorized into A, B, C, D and E categories based on titer. Categorization will be performed by IQVIA Data Management and the resulting derived data will be provided to IQVIA RWE Biostatistics. Positive/negative for NAb activity, high positive NAb activity, and NAb titer categories will be presented by study visit along with two-sided 90% and 80% Clopper-Pearson exact CIs. The titer categories are defined as follows:

- If no activity is detected upon initial testing (1:80 dilution factor) with the cell-based assay, the result is reported as category A.
- If activity is detected at the initial test concentration, the sample is retested at the same concentration (1:80 dilution factor). If no activity is detected on retest, the initial result is attributed to assay noise, and the sample is reported as category B.
- If activity is detected on both tests at MRD, the sample is diluted and retested until activity is no longer detected. Depending on the number of dilutions required to dilute NAb activity below the detectable threshold, the result is reported as follows:
  - o If no activity is detected at 1:800 dilution factor, then category C
  - o If no activity is detected at 1:8000 dilution factor, then category D
  - o If activity is detected at 1:8000 dilution factor, then category E. Dilution factors greater than 1:8000 will not be examined.

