Positive NAb activity will be defined as a titer category C, D, or E result. High positive NAb activity will be defined as a a titer category D or E result. Category D and E results are considered to represent

Document: Statistical Analysis Plan: AEGR-734-401: A 36-Month, Multicenter, Open Label Phase 4 Study to Evaluate the

Immunogenicity of Daily SC Metreleptin Treatment in Patients with Generalized Lipodystrophy

Author: [name], [name], [name], [name] Version Number: 2.1

high potency NAb activity. The clinical relevance of NAb activity results in any category has not been determined, and is a topic of current investigation. The following information will be summarized:

- Ever NAb positive and time to NAb positivity. Time to NAb positivity (months) = [((date of first NAb positive result date of baseline visit) + 1)/30.4].
- Ever high NAb positive and time to high NAb positivity. Time to high NAb positivity (months) = [((date of first hight NAb positive result date of baseline visit) + 1)/30.4].
- Peak NAb (defined as the measurement which detects NAb activity at the largest dilution factor) and time to peak NAb. Time to peak NAb activity (months) = [((date of peak NAb date of baseline visit) + 1)/30.4].

RB activity of anti-metreleptin/anti-HuL will be assessed by ECLIA receptor blocking assay and reported as follows:

- Positive/negative for RB activity by study visit. Positive RB activity is defined as RB activity detected at MRD (1:6 dilution factor). Both 90% and 80% two-sided Exact CIs will be presented.
- RB activity by study visit and titer (negative [no RB activity detected at MRD], 1:6, 1:30, 1:300, 1:3000). Dilution factors greater than 1:3000 will not be examined.
- Percent inhibition at MRD by study visit
- Ever RB positive and time to RB positivity. Time to RB positivity (months) =  $[((date \ of \ first \ RB \ positive \ result date \ of \ baseline \ visit) + 1)/30.4].$
- Peak RB (defined as the measurement which detects RB activity at the largest dilution factor) and time to peak RB. Time to peak RB result (months) = [((date of peak RB date of baseline visit) + 1)/30.4].

See **Section 8.1** Statistical Summaries, Tests and Confidence Intervals for a description of statistics to be reported.

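### The revised EAS and the per-patient antibody summaries do not exclude pre-dose results

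*SAP*

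**What the plan says.** **Analysis set.** SAP 15 states: "The primary immunogenicity analysis will be performed among the EAS". In SAP 6.3 this set held dosed subjects "who have baseline and post-dose laboratory results on the measure of interest at the time point of interest". Item 1 of the changes dated 16Dec2024 in the SAP change form replaces that with "Enrolled subjects who received at least one documented dose of metreleptin and who have at least one anti-metreleptin/anti-HuL binding antibody" result. The new text does not say when the result must have been obtained.

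**Protocol rule.** The synopsis (Statistical Methods) says "patients with a post dose sample will be assessed for immunogenicity". Protocol 10.3 asks for both baseline and post-dose data for the immunogenicity set, though it words this as efficacy data.

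**Pre-dose sample.** Under Protocol 6.2.2, the Visit 2 antibody samples "will be collected to provide a measurement prior to initiation of metreleptin". Footnote c of Protocol Table 1 places antibody sampling ahead of dosing at every visit.

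**Per-patient derivations.** SAP 15.2 lists "Ever ADA positive and time to ADA positivity" and "Ever NAb positive and time to NAb positivity", with matching items for high NAb and for receptor-blocking (RB) activity. Peak is the measurement that is still positive at the largest dilution. Every time is (date of result − date of baseline visit + 1)/30.4, and SAP Appendix 2 sets baseline as Day 0. None of these definitions is limited to samples taken after the first dose.

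**Purpose.** The synopsis (Study Population) says that only patients without previous metreleptin are to be "enrolled in order to document the development of antibodies" over time.

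**The concern.** There are two gaps, and neither depends on the other.

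(a) The revised EAS can take in a patient about whom nothing is known after dosing. If that patient's Visit 2 sample is negative, the patient counts as never positive and lowers the rate without having been observed on treatment.

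(b) The derivations let reactivity that was present before the first dose count as a positive result, set the time to positivity, and even be the peak. This gap was already in SAP 2.1: the replaced EAS required a post-dose result for entry but did not remove the baseline result from the derivations.

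The per-patient summaries condense the primary objective. With 10 patients (Protocol 10.2) or 11 (SAP 4.1), one such case is enough to set a minimum or move a rate.

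**Working it through.** **1. The plan's own interval.** Protocol 10.2 gives a 90% interval of 0.00 to 0.26 for 0 of 10. The two-sided Clopper-Pearson upper limit is 1 − 0.05^(1/10) = 0.259, which agrees. The same method is used below.

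**2. Who is admitted.** Take a dosed patient with the Visit 2 sample and nothing later.

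| Rule | Post-dose data needed? | Patient |
|---|---|---|
| Protocol synopsis | yes | out |
| Protocol 10.3 | yes, with baseline | out |
| SAP 6.3 (replaced) | yes, with baseline | out |
| Change form, 16Dec2024, item 1 | no | in |

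**3. What a pre-dose positive yields.** From the SAP 15.2 formula:
- Day 0: (0 + 1)/30.4 = 0.033 months
- Day 30: (30 + 1)/30.4 = 1.020 months

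The Day 0 value is a valid number, so nothing in the formula rejects it.

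**4. Effect of gap (a).** Table 5 of Protocol 10.2 expects 1 + 1 + 1 + 2 + 3 + 2 minus the one patient at titer 0, that is 1 + 1 + 2 + 3 + 2 = 9 of 10 patients, at titer 5 or more. I assume that titer 5 corresponds to the SAP's lowest positive step. Add one patient with only a negative pre-dose sample:
- 9/10 = 90.0% (90% CI 60.6 to 99.5; 80% CI 66.3 to 99.0)
- 9/11 = 81.8% (90% CI 53.0 to 96.7; 80% CI 58.5 to 95.1)
- Change: −8.2 points

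**5. Effect of gap (b) on the rate.** Suppose 10 of 11 are ever positive, one of them already before dosing. As planned, the rate is 10/11 = 90.9%. It stays there if that patient is counted on a later rise. With the patient listed separately it is 9/10 = 90.0%, a change of −0.9 points. In general, taking one positive out of x/n lowers the rate by (n − x)/[n(n − 1)], here 1/110. The shift is larger where fewer patients are positive.

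**6. Effect of gap (b) on time to positivity.** If ten patients turn positive at Day 30, the mean, median and minimum are all 1.020 months. With nine at Day 30 and one pre-dose positive:
- mean (9 × 1.020 + 0.033)/10 = 0.92
- median 1.02, unchanged
- minimum 0.03

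**7. Effect of gap (b) on time to peak.** Protocol 10.2 cites 4 to 7 months. Nine patients spread evenly over that range have mean 5.50, median 5.50 and minimum 4.00. Adding one pre-dose peak gives:
- mean (9 × 5.50 + 0.033)/10 = 4.95
- median (5.125 + 5.50)/2 = 5.31
- minimum 0.03

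This is an extreme case: the pre-dose titer must be at least as high as every later one.

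**8. How likely gap (b) is.** The documents give no rate of pre-dose positivity. If it were 2%, 5% or 10% per patient, the chance of at least one among 11 would be 1 − (1 − p)^11 = 20%, 43% or 69%. These rates are assumptions.

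**The case against.** The strongest reply is that no affected patient is shown and that other parts of the plan limit the harm.

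- **A rule may exist elsewhere.** The table shells and several pages of the change form were not available. This stands, and it limits how firmly the point can be put.
- **Pre-dose-only patients should be rare.** Protocol 6.3 calls for all Visit 12 assessments in early discontinuers, and Table 1 includes an antibody sample at that visit. Protocol 4.11 encourages patients who stop the drug to keep attending. This mostly stands, but a patient who withdraws consent can decline all further follow-up (Protocol 4.12.2).
- **A case would be visible.** Day 0 has its own window in the change form's Table 1, and Protocol 10.5 plans plots for each patient. These would reveal a case but would not correct the per-patient summaries.
- **The study is descriptive, and the median time to positivity does not move.** True, but SAP 8.1 also reports the mean and minimum, which do move.
- **For NAb and RB the case is narrower.** Only ADA-positive samples are tested, so the pre-dose sample would have to be reactive in both assays. This stands.
- **The SAP takes precedence over the protocol (SAP 2).** That settles which text governs. It does not supply a reason for dropping the post-dose condition.

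The other side is also right that using post-dose samples alone is not enough. Protocol 2.1 says that antibodies generally do not disappear during therapy. A baseline-positive patient would then usually test positive again at the first visit and appear as newly positive at about 1.02 months.

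**Conclusion.** The point holds on the text available, and it is minor. The revised EAS admits a dosed patient with no post-dose ADA result, contrary to the protocol and to the definition it replaced. SAP 15.2 counts a pre-dose positive as an event at 0.03 months. The sizes are illustrations that rest on Table 5 and on assumed timings: −8.2 points for one pre-dose-only negative patient, and 0 to −0.9 points for one pre-dose positive at the positivity Table 5 expects, with the main effect on the minimum and mean times.

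A reader might infer that the primary results are distorted. The documents do not support this, because they show neither a pre-dose-only nor a pre-dose positive patient. A reader might also take any very short time to positivity as proof of a pre-dose result. That does not follow either: the revised Visit 3 analysis window opens at Day 1, so a genuine post-dose sample could give (1 + 1)/30.4 = 0.07 months.

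**What to change.** For the per-patient immunogenicity summaries:

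1. Require at least one post-dose ADA result.
2. Derive ever-positive, peak and time-to for ADA, NAb and RB from post-dose samples only.
3. For each assay, take patients who are positive at baseline out of the treatment-emergent ever-positive rate and the time-to-positivity summary. List them separately with baseline and post-dose peak titers, so that persisting reactivity is not shown as new at Month 1.

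Because database lock has passed, show these beside the planned summaries, labelled supplementary and post hoc. If no patient was pre-dose-only or pre-dose positive, one sentence in the report saying so is enough.

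The cost is a few sentences in the change form or report and one derived post-dose flag, from data already collected. A patient without a post-dose sample leaves only these supplementary summaries and stays in the disposition and safety tables.
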